9.7 Randomization and Treatment Assignment

7 days or more after cDBS has been set and within 30 days after the baseline visit.

Subjects will be randomly assigned during a randomization to a subjects' preferred aDBS mode (single or dual threshold) or cDBS (BrainSense setting is ON). The randomization method is Permuted Block Randomization. The site personnel will obtain the randomization assignment via Remote Data Capture (RDC). The randomization assignment can be obtained upon completion of the Informed Consent, Inclusion/Exclusion Criteria and randomization CRFs.

Crossover is performed after 45 (± 7) days when a preferred aDBS mode (single or dual threshold) or cDBS is assigned to a subject. A subject will not have knowledge of the DBS mode assigned for the duration of the aDBS treatment phase.

The PI/Sub investigator explains to the subjects that the assigned DBS mode cannot be changed except in an emergency. If it is necessary to adjust the stimulation mode the patient needs to return to the study site to make adjustments. Visits for adjustments are recorded as unscheduled visits. All adjustments must be completed at least 14 days prior to the next visit. Any adjustments should be recorded as unscheduled visits. Any adjustments during the 14 days prior to the next visit will be considered as a protocol deviation.

In order to blind the subject to the aDBS mode assigned, PI/Sub investigator will set the group name of the preferred aDBS mode to "DBS1," the group name of cDBS to "DBS2" and the group name of non-adjusted or the non-preferred aDBS mode to "DBS3" on the Clinician Programmer. If there is another mode that has already been set, set the group name to "DBS4". These group names will be displayed on the Patient Programmer.

If blinding is broken during the aDBS treatment phase, record the reason for the blind breaking in the medical records of the subject and report it as a deviation.

9.8 aDBS Treatment Phase

This phase consists of three treatment periods [Period A initiation (Visit 1), Post Period A (Visit 2) and Post Period B (Visit 3)].

For subjects implanted a directional lead with separate electrodes (e.g., SenSight), set the output of each separate electrodes uniformly (use it as a ring-shaped electrode).

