4.2.2. Secondary Endpoint

Mean percent time within an optimal threshold of beta LFP power during aDBS mode compared to cDBS. The optimal beta LFP threshold indicates values between upper and lower beta LFP threshold preset for each patient.

5. Study Design

Prospective randomized, single-blind, crossover, multicenter study of aDBS in subjects with Parkinson's disease.

The study is expected to be conducted at two sites located in Japan. It is estimated that 20-30 subjects implanted with a commercially available Medtronic DBS system with Percept PC INS will be enrolled to obtain a study population of 20 subjects who complete the aDBS treatment phase. Participants must have either completed the Early Adapter I study, or they must have undergone a standard assessment demonstrating tolerability of aDBS (preferred mode).

There is no set minimum or maximum number of subjects to be enrolled per study site.

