9.6 Baseline

The baseline visit must occur within 30days after subject enrollment.

The PI/ Sub investigator will screen potential subjects by reviewing the study's inclusion/exclusion

criteria.

Enrolled subjects who do not meet all inclusion criteria or who meet any exclusion criteria will be discontinued from the study. No further study-related procedures will be completed, and subjects will be followed according to the site's standard procedures.

The PI/ Sub investigator will ensure the INS device time matches that of the clinician programmer tablet (network enabled). If the INS time does not match the network time, the INS time should be updated.

The following data will be collected at Baseline:

- Demographics (age, sex)*
- Medical & surgical history*
- PD history*
- Signal test (If implemented)
- Patient preference questionnaire. *
- Concomitant medications (non-PD)
- PD medication (When performing a signal test with Off PD medication, PD medication and does given at visit. Time of last dose of PD medications taken prior to the visit)
- Device identification information, including historical DBS implant information*
- Programming session upload, with device interrogation and BrainSense data included in the JSON session data report (If Signal test was implemented)
- Pre-op/post-op Magnetic Resonance Image (MRI) images and Computed Tomography (CT) images of Percept PC implant *
- AE and device deficiency assessment (As they occur)
- Protocol Deviations (As they occur)

*It is stated in the IC and consent is obtained from the subjects that these data collected prior to Early Adapter Part II are used for this study.

If both aDBS modes (single and dual threshold) are acceptable, a preference questionnaire is used to determine the preferred aDBS mode (single or dual threshold) for the subject. If the subject answers "Do not know" or "No preference" to the question "Which adaptive DBS mode do you prefer?", the PI/

Sub investigator determines the aDBS (preferred mode) which is suitable for the treatment of the patient.

The PI/ Sub investigator selects dual threshold mode from the BrainSense™ setup to set the LFP threshold if the subject's LFP threshold has not been set. The subjects who are on aDBS mode will leave the visit on cDBS settings (including BrainSense settings) in order to wash out aDBS for 7 days or more.

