For the subjects with cDBS for 7 days or more, baseline can be a stand-alone visit or can occur on the same day as the randomization/Period A initiation visit.

The PI/ Sub investigator explains to subjects that the cDBS mode cannot be changed except in an emergency. If it is necessary to adjust the stimulation the subjects need to return to the site for adjustments. Visits for adjustments are recorded as unscheduled visits.

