9.8.1. Period A initiation /Visit1

Same as Randomization day.

The PI/ Sub investigator should confirm the subject is in cDBS.

The following data will be collected:

- Concomitant medications (non-PD)
- PD medications
- Programming session upload, with device interrogation and BrainSense data included in the JSON session data report
- PDQ-39 (subject's assessment of cDBS or aDBS washout period)
- EQ-5D-5L
- MDS-UPDRS II ("best" conditions)
- MDS-UPDRS II ("worst" conditions)
- MDS-UPDRS III (On stim (cDBS)/On med) – trained rater
- MDS-UPDRS IV – trained rater
- UDysRS (subject's assessment of cDBS or aDBS washout period)
- Upload data collected from Apple Watch, including movement and sleep data (Operation confirmation)
- AE and device deficiency assessment (As they occur)
- Protocol Deviations (As they occur)

At the end of the visit, the PI/Sub investigator should program the subject to the assigned DBS mode for Period A. Start the program for Period A, and return the subject home.

Subjects will participate in a data collection of movement, sleep data and dosing cycle of PD medications with Apple Watch and iPhone. The subject will be given an Apple Watch and linked iPhone and instructed on its use. Upon receipt, the subjects should put on and activate the Apple Watch. Data collection will start immediately and will continue as long as the subject is wearing the watch and the watch is charged. After the recording, the subject will upload the data collected from Apple Watch via iPhone to the database specified by Rune Labs, Inc. Subjects will also record their PD medications in an iPhone application (STRIVE App, Rune Labs) every 14 days during Period A and Period B in aDBS treatment phase. An Apple Watch calendar will be set up to get notifications from Apple Watch for medication log. Subjects will receive further guidance on the daily charging schedule of the Apple Watch and data upload through the iPhone application (STRIVE App, Rune Labs, Inc.). Detailed procedures for the Apple Watch/iPhone data collection are outlined in the Rune Labs Study Manual. In principle, the data collected from an iPhone will be used for Data of PD medication cycle, but if the data is missing, the data recorded in a medication diary etc. can substitute by reporting in CRFs.

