9.8.3. Post Period B/Visit3

45(±7) days after Post Period A/Visit2

The PI/ Sub investigator should confirm the subject is in the assigned mode for this visit. If the subject is not in the assigned mode, a deviation CRF will be completed and the reason for the mode change will be collected. If applicable the subject will start the visit over again after 45(±7) days, where possible, i.e. if the subject tolerates well the assigned mode and the assigned mode is setup if the subject was switched to another mode by accident.

The following data will be collected:

- Concomitant medications (non-PD)
- PD medications
- Programming session upload, with device interrogation and BrainSense data included in the

JSON session data report

- PDQ-39 (subject's assessment of prior 30-day period on the assigned mode in Period B)
- EQ-5D-5L
- MDS-UPDRS II ("best" conditions)
- MDS-UPDRS II ("worst" conditions)
- MDS-UPDRS III (On stim/On med) – trained rater
- MDS-UPDRS IV – trained rater
- UDysRS (subject's assessment of prior 30-day period on the assigned mode in Period B)
- DBS Global Impression of Change score (DBS GIC)
- Patient preference questionnaire: Perform the Patient preference questionnaire of the modes assigned to period A and period B before unblinding subjects
- Patient satisfaction questionnaire: Perform the Patient satisfaction questionnaire on aDBS after unblinding subjects
- Upload data collected from Apple Watch/iPhone, including movement and sleep data *,**
- Event markers (optional)*
- AE and device deficiency assessment (As they occur)
- Protocol Deviations (As they occur)

*: Confirm if it has been done

** : In principle, the data collected from an iPhone will be used for Data of PD medication cycle, but if the data is missing, the data recorded in a medication diary etc. can substitute.

Following the end of Post period B visit, the PI/ Sub investigator breaks the blinding of a subject. For the next follow-up visit, the PI/ Sub investigator should program the subject to preferred DBS mode (aDBS or cDBS), taking into account the study subject's medical condition.

If the preferred mode is cDBS, the subject will be exited from the study following the process in section 9.15. No further study-related procedures will be completed, and subjects will be followed according to the site's standard procedures.

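### One fixed, visible label code for aDBS and cDBS, combined with subject-by-subject unblinding, leaves a minor and avoidable gap in the single blind for the patient-reported outcomes

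*Protocol*

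**What the plan says.** CIP 9.7 states that subjects are not to know their assigned mode during the aDBS treatment phase, and gives a naming rule to achieve this. The "PI/Sub investigator will set the group name of the preferred aDBS mode to" DBS1. cDBS becomes DBS2, the non-adjusted or non-preferred aDBS mode becomes DBS3, and any other mode already set becomes DBS4. The section then says: "These group names will be displayed on the Patient Programmer". The rule has no subject-specific element.

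CIP 9.8.3 sets the time of unblinding. After the Post Period B visit, "the PI/ Sub investigator breaks the blinding of a subject". This happens subject by subject, not once at the end of the study.

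On the setting, CIP 5 says "The study is expected to be conducted at two sites located in Japan", with 20 to 30 subjects enrolled. CIP 5.1 expects enrolment from 1 October 2021 to 31 December 2022. Each of the two treatment periods lasts 45 (±7) days.

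CIP 12.9 names single-blinding of subjects as one of the study's bias controls, and CIP 9.8.3 places the preference questionnaire before unblinding.

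**The concern.** A neutral label protects the blind only while its meaning is unknown. Here the meaning is the same for everyone and is disclosed to each subject in turn. Once one subject has been told which mode ran in each period, that subject knows what DBS1 and DBS2 mean on every other subject's programmer at both sites. A blinded subject who hears this can read the current mode from the screen.

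The outcomes at stake are those in which the subject's own judgement is the measurement: the Period A versus Period B preference, PDQ-39, EQ-5D-5L, MDS-UPDRS II and the UDysRS historical items, collected at Visits 2 and 3. Preference matters most, because the CIP takes care to collect it while the subject is blinded. A subject who quietly learns the code leaves nothing to observe, so the duty in CIP 9.7 to record and report a broken blind would not necessarily catch it.

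**Working it through.** The point rests on reading provisions together. The only arithmetic concerns timing.

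1. **Is the code common to all subjects?** Yes. CIP 9.7 ties each label to a mode, not to a subject, sequence or period. No other section of the CIP or SAP varies the labels or renames the groups at crossover.

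2. **Can the subject see it?** Yes, by the display statement in CIP 9.7. Exclusion criterion 1 (CIP 8.3) also requires that the subject and/or caregiver can use the patient programmer.

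3. **Can unblinding of one subject precede the end of blinding for another?** Inputs: the enrolment dates in CIP 5.1 and the period length in CIP 9.7.
   - Enrolment window: 1 October 2021 to 31 December 2022 = 456 days.
   - Blinded phase: 2 × 45 = 90 days, with limits 2 × 38 = 76 and 2 × 52 = 104 days.
   - The window is about five times the blinded phase (456 / 90 = 5.1). If entry is spread over the window, early subjects are unblinded while later ones are in Period A or B or have not begun. No provision delays unblinding until all subjects have finished.

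4. **How many subjects does this touch?** The documents cannot say, because they give neither start dates nor the split between sites. Two extremes show this.
   - If all subjects started and finished together, nobody would still be blinded when the first key was released: 0.
   - If starts were all on different days, blinded phases were equally long and both sites enrolled, everyone except the first subject at each site would finish the blinded phase after someone at the same site had been unblinded: (20 − 2) / 20 = 90%, or (30 − 2) / 30 = 93%.
   
   These are shares with an opportunity to learn the code, not shares unblinded. The step from one to the other needs information to pass between people, and the documents give no rate for that. Neither extreme is offered as an estimate.

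5. **Which results depend on the subject's blindness?**
   - TEED is computed from device-recorded currents, pulse width, frequency and impedance (CIP 12.4).
   - Percent time in the beta window comes from the device timeline (CIP 12.5.1). Neither endpoint is a subject rating.
   - Study success depends on the primary objective alone (CIP 12).
   - The patient-reported measures are additional objectives. The CIP summarises them descriptively (12.7). The SAP adds aDBS minus cDBS differences with 95% confidence intervals (7.9.3) but no tests.

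**The case against.** The strongest reply is that no consequence is shown. The labels are neutral, no contact between subjects is described and no unblinding is reported. The exposed outcomes are descriptive, and neither hypothesis test depends on them. Every subject has also already tolerated aDBS (inclusion criterion 3) and knows cDBS, so some may recognise the mode by feel whatever the screen shows. The CIP has controls as well: the assigned mode is confirmed at Visits 2 and 3, a deviation form is completed for an unassigned mode, and broken blinds are reported. A uniform code has a safety merit too, since any clinician can direct a caller to cDBS at once.

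Most of this stands, and it is why the point is minor. It does not remove the point: the listed controls would not detect hearsay, and the exposure comes from a labelling choice that is easily changed.

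A reader might infer two stronger things.

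- **That subjects can decode the label alone during washout.** Under CIP 9.6, subjects on aDBS at baseline "will leave the visit on cDBS settings (including BrainSense settings) in order to wash out aDBS for 7 days or more", and the investigator "explains to subjects that the cDBS mode cannot be changed except in an emergency". At Visit 1, "The PI/ Sub investigator should confirm the subject is in cDBS". A subject who saw DBS2 while knowingly on cDBS would have the key. But the naming rule sits under randomization, and CIP 9.8.1 dates Visit 1 as "Same as Randomization day". The natural reading is that names are set only then, although the CIP does not state the time. CIP 9.6 also lets subjects already on cDBS for at least 7 days have baseline on the randomization day, so their earlier cDBS time precedes any study naming. The route is conditional and cannot apply to every subject.
- **That CIP 10.2 permits free switching during the blinded phase.** It says a subject with uncomfortable stimulation can move from aDBS to cDBS as needed. That is a study-wide risk statement. CIP 9.7 is the specific rule for the blinded phase and already has an emergency exception. No change to 10.2 is needed.

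**Conclusion.** The point holds as a minor design weakness. The code is the same for all subjects, is displayed to them, and is disclosed one subject at a time, so each unblinding releases a key that also fits the rest. The consequence is limited to the credibility of the blinded patient-reported additional outcomes, chiefly preference.

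The conclusion assumes that entry is staggered, as the length of the enrolment window suggests, and that some information could reach a blinded subject. The documents establish neither how often that would happen nor in which direction it would move any score, so no size of bias can be given. A reader should not infer that the blind failed or that the TEED or beta-window comparison is compromised. The text supports neither.

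**What to change.** In CIP 9.7, break the fixed link between label and mode for DBS1 and DBS2 only. Either of these would do:

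- the remote data capture system issues, with the sequence assignment, a random subject-specific mapping of DBS1 and DBS2 to the two modes; or
- the groups are named by period, with the Period A mode as DBS1 and the Period B mode as DBS2. All subjects then see the same labels in the same order, and the sequence assignment is the key.

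Keep DBS3 and DBS4 fixed. DBS3 may be a non-adjusted or non-preferred aDBS mode, and a look-up error must not send a distressed subject there. State that the names are applied only at the start of Period A, which also closes the washout question. Keep the key at the site for emergencies.

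This is a cheap improvement: no extra subjects, visits or change of analysis. It needs a CIP revision, with ethics committee approval before use at a site (CIP 14.7), and subjects already labelled keep the current code. The downsides are slightly more risk of a programming error and a short look-up before telling a caller which group selects cDBS. Recognition by sensation remains possible, so the gain may be modest.

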9.8.1. Period A initiation /Visit1

Same as Randomization day.

The PI/ Sub investigator should confirm the subject is in cDBS.

The following data will be collected:

- Concomitant medications (non-PD)
- PD medications
- Programming session upload, with device interrogation and BrainSense data included in the JSON session data report
- PDQ-39 (subject's assessment of cDBS or aDBS washout period)
- EQ-5D-5L
- MDS-UPDRS II ("best" conditions)
- MDS-UPDRS II ("worst" conditions)
- MDS-UPDRS III (On stim (cDBS)/On med) – trained rater
- MDS-UPDRS IV – trained rater
- UDysRS (subject's assessment of cDBS or aDBS washout period)
- Upload data collected from Apple Watch, including movement and sleep data (Operation confirmation)
- AE and device deficiency assessment (As they occur)
- Protocol Deviations (As they occur)

At the end of the visit, the PI/Sub investigator should program the subject to the assigned DBS mode for Period A. Start the program for Period A, and return the subject home.

Subjects will participate in a data collection of movement, sleep data and dosing cycle of PD medications with Apple Watch and iPhone. The subject will be given an Apple Watch and linked iPhone and instructed on its use. Upon receipt, the subjects should put on and activate the Apple Watch. Data collection will start immediately and will continue as long as the subject is wearing the watch and the watch is charged. After the recording, the subject will upload the data collected from Apple Watch via iPhone to the database specified by Rune Labs, Inc. Subjects will also record their PD medications in an iPhone application (STRIVE App, Rune Labs) every 14 days during Period A and Period B in aDBS treatment phase. An Apple Watch calendar will be set up to get notifications from Apple Watch for medication log. Subjects will receive further guidance on the daily charging schedule of the Apple Watch and data upload through the iPhone application (STRIVE App, Rune Labs, Inc.). Detailed procedures for the Apple Watch/iPhone data collection are outlined in the Rune Labs Study Manual. In principle, the data collected from an iPhone will be used for Data of PD medication cycle, but if the data is missing, the data recorded in a medication diary etc. can substitute by reporting in CRFs.

The PI/Sub investigator will set up a maximum of 4 event types, selected from the following options: dyskinesia, tremor, rigidity, freezing, sleep disturbance, took PD medication to collect Events with LFP capture (Event markers). PI/Sub investigator should instruct the subject on how to record each event type utilizing the Patient Programmer System.

9.8.2. Post Period A /Visit2

45(\pm 7) days after Period A/Visit1

The PI/ Sub investigator should confirm the subject is in the assigned mode for this visit. If the subject is not in the assigned mode, a deviation CRF will be completed and the reason for the mode change will be collected. If applicable the subject will start the visit over again after 45(\pm 7) days, where possible, i.e. if the subject tolerates well the assigned mode the assigned mode is setup, and if the subject was switched to another mode by accident.

The following data will be collected:

- Concomitant medications (non-PD)
- PD medications
- Programming session upload, with device interrogation and BrainSense data included in the JSON session data report
- PDQ-39 (subject's assessment of prior 30-day period on the assigned mode in Period A)
- EQ-5D-5L

- MDS-UPDRS II ("best" conditions)
- MDS-UPDRS II ("worst" conditions)
- MDS-UPDRS III (On stim/On med) – trained rater
- MDS-UPDRS IV – trained rater
- UDysRS (subject's assessment of prior 30-day period on the assigned mode in Period A)
- DBS Global Impression of Change score (DBS GIC)
- Upload data collected from Apple Watch/iPhone, including movement and sleep data *,**
- Event markers (optional)*
- AE and device deficiency assessment (As they occur)
- Protocol Deviations (As they occur)

*: Confirm if it has been done

** : In principle, the data collected from an iPhone will be used for Data of PD medication cycle, but if the data is missing, the data recorded in a medication diary etc. can substitute.

At the end of the Post period A visit, the PI/Sub investigator should program the subject to the assigned DBS mode for Period B. Start the program for Period B, and return the subject home .

9.8.3. Post Period B/Visit3

45(±7) days after Post Period A/Visit2

The PI/ Sub investigator should confirm the subject is in the assigned mode for this visit. If the subject is not in the assigned mode, a deviation CRF will be completed and the reason for the mode change will be collected. If applicable the subject will start the visit over again after 45(±7) days, where possible, i.e. if the subject tolerates well the assigned mode and the assigned mode is setup if the subject was switched to another mode by accident.

The following data will be collected:

- Concomitant medications (non-PD)
- PD medications
- Programming session upload, with device interrogation and BrainSense data included in the

JSON session data report

- PDQ-39 (subject's assessment of prior 30-day period on the assigned mode in Period B)
- EQ-5D-5L
- MDS-UPDRS II ("best" conditions)
- MDS-UPDRS II ("worst" conditions)
- MDS-UPDRS III (On stim/On med) – trained rater
- MDS-UPDRS IV – trained rater
- UDysRS (subject's assessment of prior 30-day period on the assigned mode in Period B)
- DBS Global Impression of Change score (DBS GIC)
- Patient preference questionnaire: Perform the Patient preference questionnaire of the modes assigned to period A and period B before unblinding subjects
- Patient satisfaction questionnaire: Perform the Patient satisfaction questionnaire on aDBS after unblinding subjects
- Upload data collected from Apple Watch/iPhone, including movement and sleep data *,**
- Event markers (optional)*
- AE and device deficiency assessment (As they occur)
- Protocol Deviations (As they occur)

*: Confirm if it has been done

** : In principle, the data collected from an iPhone will be used for Data of PD medication cycle, but if the data is missing, the data recorded in a medication diary etc. can substitute.

Following the end of Post period B visit, the PI/ Sub investigator breaks the blinding of a subject. For the next follow-up visit, the PI/ Sub investigator should program the subject to preferred DBS mode (aDBS or cDBS), taking into account the study subject's medical condition.

If the preferred mode is cDBS, the subject will be exited from the study following the process in section 9.15. No further study-related procedures will be completed, and subjects will be followed according to the site's standard procedures.

